9.1.1.2 Expansion (Part 2)

Prior to starting Part 2 of the study, the investigators and the Sponsor will use safety, efficacy, PK, and pharmacodynamic data obtained during the Dose Escalation Phase, as well as clinical judgement, to jointly determine the dose schedules to be studied.

During Part 2, the Dose Expansion phase, approximately 40 subjects per dose schedule will be enrolled to examine QD and/or BID dose schedules. Subjects enrolled into Part 2, Dose Expansion phase, must be FGF19-positive as defined by Sponsor-designated laboratory.

Part 2 of the study is designed to better characterize the safety, tolerability and preliminary antitumor activity of the study drug when provided at the RP2D and schedule. For a reference of the precision of objective response rate (ORR) estimates, the associated 2-sided 95% CIs for ORR up to 30% for 40 subjects is provided. See [Section 9.7.2](#) for additional

information. When both dose schedules are accruing subjects, an alternating enrollment schema into QD and BID dose schedule will be followed.

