9.4.4 Method of Assigning Subjects to Treatment Groups

The dose level to which a subject is assigned is dependent on the study part and cohort into which the subject is enrolled.

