9.4.7 Blinding

The study will not be blinded.

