9.7.1.1 Study Endpoints

The primary study endpoints are:

- Occurrence of DLTs as a function of the dose of H3B-6527 for determination of the MTD and RP2D.
- Safety/tolerability: the type and frequency of AEs, SAEs using CTCAE, Version 4.03, as well as changes in clinical laboratory values, ECG parameters, and vital sign measurements.

Secondary study endpoints are:

- PK: standard primary PK parameters including, but not limited to, the area under the plasma concentration-time curve from time 0 through the last measurable point (AUC_{0-t}), maximum observed plasma concentration (C_{max}) and time of maximum observed plasma concentration (t_{max}).
- Preliminary antitumor activity: Response will be determined by the investigator using mRECIST ([Appendix 1](#)). The following endpoints will be determined:

- ORR, defined as the proportion of subjects achieving a best overall confirmed response of partial response (PR) or CR (PR + CR), from first dose date until disease progression/recurrence.
- Duration of response, defined as the time from the date of first documented CR/PR until the first documentation of disease progression as determined by the investigator or death, whichever comes first.
- Progression-free survival (PFS), defined as the time from first dose date to the date of the first documentation of disease progression as determined by the investigator or death (whichever occurs first).
- Overall survival (OS), defined as the time from first dose date to the date of death.
- Time to response, defined as the time from first dose date to the date of first documented CR/PR.

Exploratory study endpoints include:

- Correlation of biomarker expression levels with antitumor activity and safety
- Expression levels of biomarkers in blood and tumor samples
- Correlation of biomarker expression levels with H3B-6527 exposure in plasma
- H3B-6527 levels in tumor tissue may be assessed
- H3B-6527 metabolites in plasma and urine

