12.5% (5 responders in 40 subjects)	(0.042, 0.268)
15% (6 responders in 40 subjects)	(0.057, 0.298)
17.5% (7 responders in 40 subjects)	(0.073, 0.328)
20% (8 responders in 40 subjects)	(0.091, 0.356)
22.5% (9 responders in 40 subjects)	(0.108, 0.385)
25% (10 responders in 40 subjects)	(0.127, 0.412)
27.5% (11 responders in 40 subjects)	(0.146, 0.439)
30% (12 responders in 40 subjects)	(0.166, 0.465)

CI = confidence interval, ORR = objective response rate.

Within each treatment arm, if both QD and BID dose schedules are studied, an evaluation using efficacy, safety, PK, pharmacodynamic data will be performed and the investigators and Sponsor will jointly determine if one dose schedule is better than the other.

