### **Dose Expansion Phase (Part 2)**

A total of approximately 40 to 80 subjects will be enrolled in the Dose Expansion phase. Prior to starting the Dose Expansion phase, the investigators and the Sponsor will use safety, efficacy, PK, and pharmacodynamic data obtained during the Dose Escalation Phase, as well as clinical judgement, to jointly determine the dose schedules to be studied.

During Part 2, the Dose Expansion phase, a sample size of 40 evaluable subjects per dose schedule will be enrolled to examine QD and/or BID dosing of H3B-6527 based on the recommended dose determined from Part 1 (Table 3). For a reference of the precision of ORR estimates, the associated 2-sided 95% CIs for ORR up to 30% (40 subjects) are provided in Table 4.

This study makes provision for exploring a BID schedule of H3B-6527 during the Dose Expansion phase if evaluation of the PK, pharmacodynamics, or safety of H3B-6527 suggests that it may be preferable to administer H3B-6527 BID rather than QD. When both dose schedules are accruing subjects, an alternating enrollment schema into QD and BID schedule will be followed.

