**Table 4. 2-sided 95% CI for ORR estimate up to 30% (40 subjects)**

ORR (N=40)	2-sided 95% CI
5% (2 responders in 40 subjects)	(0.006, 0.169)
7.5% (3 responders in 40 subjects)	(0.016, 0.204)
10% (4 responders in 40 subjects)	(0.028, 0.234)
12.5% (5 responders in 40 subjects)	(0.042, 0.268)
15% (6 responders in 40 subjects)	(0.057, 0.298)
17.5% (7 responders in 40 subjects)	(0.073, 0.328)
20% (8 responders in 40 subjects)	(0.091, 0.356)
22.5% (9 responders in 40 subjects)	(0.108, 0.385)
25% (10 responders in 40 subjects)	(0.127, 0.412)
27.5% (11 responders in 40 subjects)	(0.146, 0.439)
30% (12 responders in 40 subjects)	(0.166, 0.465)

Within each treatment arm, if both QD and BID dose schedules are studied, an evaluation using efficacy, safety, PK, pharmacodynamic data will be performed and the investigators and Sponsor will jointly determine if one dose schedule is better than the other.

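### If QD and BID accrue together in Part 2, open-label alternation with no stated concealment leaves the planned judgement between schedules open to selection bias

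*Protocol*

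**What the plan says.** **Allocation.** Under Protocol Section 9.1.1.2, while both schedules are open, "an alternating enrollment schema into QD and BID dose schedule will be followed". The synopsis and Sections 9.1 and 9.7.2 repeat the rule, as do SAP Sections 3.2.3 and 4 ("an alternating enrollment schema into QD and BID schedule will be followed"). The assignment section, 9.4.4, adds only this: "The dose level to which a subject is assigned is dependent on the study part and cohort into which the subject is enrolled". Neither document describes randomisation, central assignment or concealment for Part 2.

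**Blinding and assessment.** Section 9.4.7: "The study will not be blinded". Section 9.7.1.1: "Response will be determined by the investigator using mRECIST".

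**Use of the two arms.** If both schedules are studied, Section 9.7.2 plans an evaluation that draws on PK and pharmacodynamic results as well as efficacy and safety, after which "the investigators and Sponsor will jointly determine if one dose schedule is better than the other". SAP Section 4 repeats this below its Table 4 ("Sponsor will jointly determine if one dose schedule is better than the other"). No method of comparison is given, and SAP Section 5.3.2 marks covariate adjustment as not applicable.

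**When it applies.** Section 9.3 makes the size of Part 2 depend on whether the escalation data clearly separate the schedules. If they do, one schedule may go forward with 40 subjects; if not, both continue with 40 each.

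**The concern.** Alternation is deterministic. Anyone who knows the last assignment in the sequence knows the next one, and in an open-label study treatment is not hidden. A site that knows which schedule comes next can bring a subject forward, hold one back, or change the order of two candidates. The arms can then differ in prognosis before the first dose.

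The arms are also meant to be compared. Both run only when Part 1 has not settled the choice of schedule, so Part 2 becomes the main evidence for that choice. A gap produced by enrolment order could be read as an effect of schedule. Baseline tables by schedule would show measured imbalances, but they would not correct them and cannot show unmeasured ones.

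**Working it through.** **1. The plan's own precision figure.** Protocol Table 9 (SAP Table 4) gives (0.166, 0.465) for 12 responders in 40. The exact Clopper-Pearson limits are 0.1656 and 0.4653, so the figure reproduces. It describes precision within one schedule. Neither document gives power or an effect size for QD against BID.

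**2. Sampling error of the difference.** With 40 per schedule and an assumed ORR of 20% in both, the 95% half-width is 1.96 × √(2 × 0.2 × 0.8 / 40) = 0.175, or about 17.5 points.

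**3. Who could know the next assignment.** Section 6 of the Protocol plans about 40 sites, and Part 2 has at most 80 subjects: 80 / 40 = 2 per site on average if all sites take part.

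- *Alternation within a site:* every assignment after the site's first follows from its own record. With 40 sites that is 80 − 40 = 40 of 80 subjects, and more if fewer sites recruit or the starting arm is known.
- *Alternation across the study:* a site would need to know the latest assignment elsewhere.

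The documents do not say which is meant, or whether the sequence is kept from sites.

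**4. Illustrative bias.** The documents give no inputs for this, so these are assumptions. Half the subjects have a good prognosis (response rate g) and half a poor one (rate b), with no true schedule effect. If a share s of subjects is steered by prognosis, the favoured arm contains 0.5 + s/2 good-prognosis subjects and the other arm 0.5 − s/2. The false ORR difference is s × (g − b). The last two columns give the binomial probability that the favoured arm shows at least 4 more responders out of 40 (10 points).

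| Steered share s | Bias, 25%/15% | Bias, 30%/10% | P(≥4 more), 25%/15% | P(≥4 more), 30%/10% |
|---|---|---|---|---|
| 0 | 0 | 0 | 16% | 16% |
| 10% | 1 point | 2 points | 19% | 22% |
| 20% | 2 points | 4 points | 22% | 30% |
| 40% | 4 points | 8 points | 30% | 47% |

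For example, with s = 40% and 30%/10%, the arm rates are 0.7 × 0.30 + 0.3 × 0.10 = 24% and 0.3 × 0.30 + 0.7 × 0.10 = 16%.

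**5. What randomisation changes.** For an observer who sees every earlier assignment, the expected share of correct guesses is 100% under alternation and 50% under simple randomisation. With permuted blocks of known size 4, 6 or 8 it is 71%, 68% or 67%. The excess over chance falls from 50 points to about 17 to 21, and further when block size is withheld. The sample size and the Table 9 precision do not change.

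**The case against.** The strongest reply is that this is a conditional, informal comparison in a Phase 1 study. Alternation applies only if both schedules accrue together. No objective or endpoint contrasts QD with BID, the sample size rests on precision within a schedule, and there is no hypothesis test. The sentence that announces the judgement is also unclear: it speaks of both schedules within each treatment arm, while Table 8 defines the arms as QD and BID. This sets the scope. It does not remove the concern, because an informal choice of schedule can be biased as easily as a formal one.

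A second reply is practical. At about 2 subjects per site, study-wide alternation would be hard to predict. Enrolment also waits for a fresh biopsy, a laboratory FGF19 result and a 28-day screening window within 8 weeks overall (Section 9.5.1.1.1). This stands as a reason to doubt heavy steering: a 40% share means 0.4 × 80 = 32 subjects. It does not rule out lighter steering, and a safeguard that the plan does not state cannot be relied on.

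A third reply is that random error dominates. Even 8 points is less than half of 17.5, and power for 20% against 30% ORR with 40 per arm is only 12% (Fisher exact) to 18% (z test). That is correct. But the bias has a direction, no interval includes it, and it can be avoided without more subjects.

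A reader might go further and infer that every assignment is known in advance, that type I error is inflated, or that randomisation would remove the bias altogether. The documents do not support the first, because the level of alternation is unstated, or the second, because no test is planned. The third fails because some assignments stay guessable in an open-label study and the investigator still assesses response unblinded.

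**Conclusion.** The concern holds in a limited form. If both schedules accrue in Part 2, the plan allocates by a deterministic rule with no stated concealment and then uses the arms to judge which schedule is better. The risk is a biased informal choice of schedule. The ORR estimate and interval within each schedule keep their stated statistical precision.

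Under the assumed strata and 10% to 40% steering, the bias is about 1 to 8 ORR points, against a sampling half-width of about 17.5. These sizes are illustrations: the steered share and the stratum response rates come from no source in the documents, and only ORR is modelled, while the planned judgement also uses safety, PK and pharmacodynamic data. How likely steering is depends mainly on whether alternation runs within sites or across them. The change is worth making because it is modest and costs no sample size.

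**What to change.** While both schedules accrue, replace alternation with central 1:1 randomisation in permuted blocks, with block sizes not disclosed to sites. Keep 40 per schedule, the visits and a descriptive analysis. Make the change wherever the alternation rule appears: Protocol synopsis and Sections 9.1, 9.1.1.2 and 9.7.2, and SAP Sections 3.2.3 and 4. State the method in Protocol Section 9.4.4. In the same edit, reword the sentence after Table 9 so that it refers to a comparison between the QD and BID arms.

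If alternation is kept, state whether it runs by site or across the study and who can see the sequence, and label any schedule comparison as non-randomised and descriptive.

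**Cost.** A randomisation list, a central assignment step and an amendment. Protocol Section 11.1 requires health authority submission and ethics approval for amendments that affect scientific quality, here across about 40 sites. Blocks may leave an imbalance of a few subjects if one arm closes early. If Part 2 has already started, subjects allocated by alternation should be identified in the summaries. Response assessment would remain unblinded, and the report should say so.

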9.1.2 Study Phases

The study will be conducted in the following 4 phases: Pretreatment Phase, Treatment Phase, Extension Phase, and Follow-up Phase.

9.1.2.1 Pretreatment Phase

This pretreatment phase will last no longer than 28 days and includes:

- **A Screening Period** to establish protocol eligibility.
- **A Baseline Period** to establish disease characteristics before treatment.

9.1.2.2 Treatment Phase

The Treatment Phase will last for 1 treatment cycle of 21 days.

Subjects who are receiving study drug at the end of the Treatment Phase will continue to receive study drug in the Extension Phase (see Section 9.1.2.3).

9.1.2.3 Extension Phase

In the Extension Phase, subjects will continue to receive the same treatment and dose they received during the Treatment Phase, provided termination criteria are not met.

In both the Treatment and Extension Phases, subjects will discontinue study drug at the time of progressive disease (PD), development of unacceptable toxicity, withdrawal of consent, or termination of the study program by the Sponsor. However, subjects may continue to receive study treatment, as long as there is demonstrated clinical benefit, as judged by the investigator after discussion with the Sponsor, or until the end of the study. Disease progression will be determined by the investigator following relevant modified Response Evaluation Criteria in Solid Tumors (mRECIST) guidelines. The mRECIST for this protocol harmonizes the original mRECIST criteria ([Lencioni and Llovet 2010](#)) using triphasic liver CT/magnetic resonance imaging (MRI; optimized for precontrast, arterial phase, and portal venous phase) and elements of Response Evaluation Criteria in Solid Tumors, Version 1.1 ([Eisenhauer, et al., 2009](#)).

9.1.2.4 Follow-Up Phase

After the Off-treatment Visit (OTV), all subjects who discontinue study treatment, regardless of their reasons for doing so, will be followed for survival via telephone (for those subjects who experience PD or initiate a new anticancer therapy) or office visit (for those subjects still undergoing tumor assessments). Subjects will be followed for survival approximately every 12 weeks for up to 12 months or until 6 cycles after last patient in, death, loss to follow-up, or withdrawal of consent, whichever occurs first. Subjects who discontinue study drug and

have not experienced PD will continue to undergo tumor assessments every 6 weeks until documented PD or another anticancer therapy is initiated.

The data cutoff for the primary analysis will occur once the last subject completes 6 cycles of investigational therapy. Subjects will be allowed to continue treatment until progression or the end of therapeutic benefit from the study drug as determined by Sponsor discussion with investigator.

The end of the study is defined as when the last ongoing subject completes their off treatment visit. The off treatment visit should occur 30 days after final dose with a window of ± 3 days.

The maximum estimated period for each subject on treatment is anticipated to be approximately 4 months. However, subjects may continue to receive study treatment, as long as they demonstrate clinical benefit as judged by the investigator after discussion with the Sponsor or until the end of the study.

9.2 Discussion of Study Design, Including Choice of Control Groups

The goals of Phase 1 oncology studies include estimation of the initial safety and tolerability of a study drug, establishment of an MTD, and determination of a recommended range of doses for evaluation in future clinical studies, based on PK and pharmacodynamic effects (Ahn, 1998; ICH E8, 1997; Gatsonis and Greenhouse, 1992; Dillman and Koziol, 1992); the primary objectives of the current study are consistent with those typical of Phase 1 oncology studies.

During the Dose Escalation Phase of the study, a traditional 3+3 dose escalation design will be used. The dose escalation scheme to be followed is based on a modified Fibonacci sequence schema, which is commonly employed in Phase 1 dose-finding oncology studies (Storer, 1989). An integrated evaluation of safety, tolerability, PK, and pharmacodynamic data will be utilized to select the RP2D dose schedule to be employed during the Dose Expansion phase.

Preliminary assessment of activity or potential therapeutic benefit may be a secondary objective of Phase 1 studies (ICH E8, 1997). Consistent with this premise, a secondary objective is to evaluate the potential antitumor activity of H3B-6527. After identification of the MTD, the potential antitumor activity of H3B-6527 will be evaluated in Part 2, the Expansion phase, to determine whether there are any tolerability issues or antitumor activity associated with the use of H3B-6527 in subjects with HCC.

It is recommended that the effect of food intake on the rate and extent of absorption of an orally administered investigational drug be investigated as early as possible during drug development to optimize dose finding and to ensure optimal food recommendations for study drug administration. The decision was made to allow study drug administration in conjunction with a meal, and this was informed by the Healthy Volunteers Food-Effect study (H3B-6527-A001-001). The starting dose of study drug when given with food was agreed upon with the SRC to meet the criteria that it be no more than one-half of the previously

determined safe total daily dose level. Any additional dose escalation will follow the procedures outlined in [Section 9.1.1](#).

Since the study drug is to be administered with food, all subjects will be required to fast 2 hours prior to pharmacodynamic assessments and have a meal prior to or in conjunction with study drug administration.

9.3 Selection of Study Population

Approximately 30 to 128 subjects are planned to be enrolled in this study: 30 to 48 during Part 1, the Dose Escalation phase, and up to 80 subjects in the Expansion phase (40 subjects per dose schedule). The total number of subjects to be enrolled in the Dose Escalation phase will be dependent upon the observed safety profile, which will determine the number of subjects per dose cohort, as well as the number of dose escalations required to achieve the MTD of H3B-6527 and establish the RP2D. The total number of subjects in the Dose Expansion Phase will be dependent on whether data collected during the Dose Escalation Phase of the study can clearly differentiate between one dosing schedule (QD or BID) or whether both schedules will continue being evaluated during the Dose Expansion phase.

Subjects who do not meet all the inclusion criteria or who meet any of the exclusion criteria will not be eligible for enrollment in the study.

9.3.1 Inclusion Criteria

In order to be eligible for participation in this study, subject must:

1. Be ≥ 18 years of age.
2. Have an Eastern Cooperative Oncology Group (ECOG) Performance Status of 0 or 1.
3. Have an HCC diagnosis with the following criteria:
 - Confirmed by available pathology records or current biopsy (confirmed diagnosis may be made by histological examination or by noninvasive criteria according to the European Association for the Study of the Liver or the American Association for the Study of Liver Disease Guidelines)
 - Advanced, unresectable, or recurrent
 - Progressing since the last antitumor therapy
 - Child-Pugh A classification
 - No clinically significant ascites
 - Must have received at least one prior standard-of-care therapy, unless contraindicated.
4. Must be FGF19-positive, as determined by a Sponsor-designated laboratory from a fresh tumor sample prior to enrollment in the Dose Expansion phase.
5. Have completed any prior chemotherapy, monoclonal antibody or immunotherapy (eg, tumor vaccine, cytokine, or growth factor given to control the cancer) at least 4 weeks or

5 half-lives (whichever is shorter) before study drug administration, and all AEs must have either returned to Baseline or resolved to Grade 0 or 1.

6. Have completed any prior definitive radiation therapy at least 3 weeks before study drug administration; any prior focal radiotherapy at least 2 weeks before study drug administration; and irradiated lesions should show evidence of size increase as defined in inclusion criterion #7 if they are intended to be followed as target lesions; any radiopharmaceutical therapy (strontium, samarium, and yttrium) must have been completed 8 weeks before study drug administration.
7. Have tumor tissue available as follows:
 - a. Part 1, Dose Escalation: Tumor tissue (screening acquisition or archival tissue if available) is requested but not mandated.
 - b. Part 2, Dose Expansion: Fresh tumor tissue must be available (collected up to 8 weeks before administration of H3B-6527 on C1 Day 1). Archival tissue if available is requested but not mandated.
8. Have measurable disease as follows:
 - a. Part 1, Dose Escalation: Subjects may have measurable or nonmeasurable disease as defined by mRECIST.
 - b. Part 2, Expansion: Subjects must have measurable disease meeting the following criteria:
 - i. Subjects with HCC: At least 1 measurable target lesion according to mRECIST that meets the following criteria:
 - Hepatic lesion
 - The lesion can be accurately measured in at least one dimension as ≥ 1.0 cm
 - The lesion is suitable for repeat measurement
 - The lesion shows intratumoral arterial phase enhancement on contrast-enhanced CT or MRI
 - Nonhepatic lesion
 - Lymph node lesion that measures at least one dimension as ≥ 1.5 cm in the short axis, except for porta hepatis lymph node that measures ≥ 2.0 cm in the short axis
 - Non-nodal lesion that measures ≥ 1.0 cm in the longest diameter
9. Have left ventricular ejection fraction $>50\%$ on echocardiography or multiple-gate acquisition (MUGA) scan.
10. Have adequate renal function defined as serum creatinine $<1.5 \times \text{ULN}$ (or calculated creatinine clearance ≥ 50 mL/min per the Cockcroft and Gault formula).
11. Have adequate bone marrow function including:

- a. Absolute neutrophil count (ANC) $\geq 1500/\text{mm}^3$ ($\geq 1.5 \times 10^9/\text{L}$)
- b. Platelet counts $\geq 75,000/\text{mm}^3$ ($\geq 75 \times 10^9/\text{L}$)
- c. Hemoglobin $\geq 9.0 \text{ g/dL}$ (may have been transfused)

12. Have adequate liver function including:

- a. Adequate blood coagulation as evidenced by an International Normalized Ratio ≤ 1.5 .
- b. Total bilirubin $\leq 1.5 \times \text{ULN}$.
- c. ALT and AST $\leq 5 \times \text{ULN}$.
- d. No evidence of biliary duct obstruction unless obstruction controlled by local treatment or, the biliary tree can be decompressed by endoscopic or percutaneous stenting with subsequent reduction in bilirubin to $\leq 1.5 \times \text{ULN}$.

13. Females must not be lactating or pregnant at Screening or Baseline (as documented by a negative beta-human chorionic gonadotropin [β -hCG] test with a minimum sensitivity of 25 IU/L or equivalent units of β -hCG). A separate baseline assessment is required if a negative screening pregnancy test was obtained more than 72 hours before the first dose of study drug.

NOTE: All females will be considered to be of childbearing potential unless they are postmenopausal (amenorrheic for at least 12 consecutive months, in the appropriate age group and without other known or suspected cause) or have been sterilized surgically (ie, bilateral tubal ligation, total hysterectomy or bilateral oophorectomy, all with surgery at least 1 month before dosing).

14. Females of childbearing potential should avoid becoming pregnant and use highly effective contraception while on treatment and for at least 1 month after finishing treatment. Females of childbearing potential must not have had unprotected sexual intercourse within 30 days before study entry and must agree to use a highly effective method of contraception (eg, sexual abstinence, an intrauterine device, a contraceptive implant, an oral contraceptive, or have a vasectomized partner with confirmed azoospermia) throughout the entire study period and for 30 days after study drug discontinuation. Sexual abstinence is considered a highly effective method only if defined as refraining from heterosexual intercourse during the entire period of risk associated with the study treatment. The reliability of sexual abstinence needs to be evaluated in relation to the duration of the clinical study and the preferred and usual lifestyle of the subject. Periodic abstinence (calendar, symptothermal, and post-ovulation methods), withdrawal (coitus interruptus), spermicides only, and lactational amenorrhea method are not acceptable methods of contraception. Female condom and male condom should not be used together. Females who are using hormonal contraceptives must have been on a stable dose of the same hormonal contraceptive product for at least 4 weeks before dosing and must continue to use the same contraceptive during the study and for 30 days after study drug discontinuation. Women using oral hormonal contraceptives should add a barrier method.

15. Be willing and able to comply with all aspects of the protocol.

16. Provide written informed consent prior to any study-specific Screening procedures.

